11.2 Analysis populations

Analysis of all efficacy variables will be performed only for patients who completed the study without protocol violation (as per protocol).

Analysis of all safety variables will be performed for all patients (intent-to-treat population) who received even 1 dose of the treatment; either Ursoplus[®] capsules or UDCA or Placebo.

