Vital Signs & Weight:

Weight: _____ Kg

Blood Pressure (Systolic/Diastolic): ____ / ___ mmHg

Physical Examination

*Please fill the relevant forms of adverse events in case any untoward or unusual event that occurred since last visit, whether it is believed to be related to the study drug or not.

Physical Examination	Normal	Abnormal	
Findings		 	

Is the participant taking any	No Yes		
concomitant medications?	If Yes: Complete Concomitant Medication		
conconnitant medications :	Page 26		

Is the participant had any Adverse Events

The investigator shall ask probing questions, allowing the patient to tell about any untoward or unusual event that occurred since the last visit, whether he/she (the patient) believes it is related to the study drug or not? (including abnormal physical examination/ laboratory results)		Complete 30
---	--	-------------

I have updated the AEs on page And have assessed them for seriousness, causality, severity and outcome and confirm that, to the best of my knowledge, it accurately reflects the study information obtained for this participant:

Investigator's Name:

Investigator's Signature: _____ Date: ____/ ____/

(DD / MMM / YYYY)	
-------------------	--

Patient's Nº:			Patient's Initials:			Study Completion page
Study Completion						
Did participant	complete	the trial?				
Yes, Please pro	ovide date of	f last day:				
/ / 2 0 (DD / MMM / YYYY)						
No, Please provide date of withdrawal and complete below:						
/	/20		(DD / I	MMM / YYY	Y)	
Early Withdrawa trial:	al: please	tick mos	t appropriate r	eason for p	particip	ant not completing the
Adverse Events related: please state related AE:(add details to AE page)						
Participant's decision, specify:						
☐ Investigator's decision, specify:						
Sponsor's decision						
□ Lost to follow up						
Patient deceased						
☐ Ineligibility (either arising during the study or retrospective having been overlooked at screening)						
Significant protocol deviation						
Significant non-compliance with treatment regimen or study requirements						
Disease progression which requires discontinuation of the study medication or results in inability to continue to comply with study procedures						
Consent with	hdrawn.					
Pregnancy or discontinuation of contraception						
Other, specify:						
Investigator Sig	jn off					
Investigator's N	lame:					
Investigator's S	ignature:				 D / MMM ;

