2 STUDY DESIGN

This is a Prospective, Multi center, open-label, randomized, control, Interventional, phase IV Study will be conducted in 2 sites in Egypt; the Research Center of Air Force Specialized Hospital and Helwan University Hospital to assess the efficacy & safety of Ursoplus® capsules (UDCA 250mg & Silymarin 140mg) versus UDCA alone versus Placebo among compensated Chronic Liver Disease Patients.

This study is a clinical trial that will enroll 297 patients, based on Vibration-controlled transient elastography in screening visit; subjects will be enrolled in 2 groups:

- Group 1: with non-cirrhosis, F0, F1 and F2.
- Group 2: with advanced fibrosis and cirrhosis, F3 and F4

Subjects in each group (1 or 2) will be treated with either:

- Ursoplus[®] capsules (group A),
- Ursofalk® capsules (UDCA 250mg); group B (control group 1):
- Or with Placebo, in group C (control group 2), using Stratified random sampling

Generated by Data Management department (DM) of the CRO (Nagy Research) for the 3 treatment groups with a ratio of 1: 1:1. Subjects who will be enrolled in this study will agree to the release of information and sign an informed consent. Subjects included in this study are enrolled for the collection of data that reflect the care they receive under routine clinical circumstances. All provided care should be according to protocol and the local standard of medical care.

The screening and enrollment period is planned to be 6 months. The total duration of the study/subject will be 6 months for treatment, follow-up, and End of Study visits

3 Inclusion and Exclusion Criteria:

3.1 Inclusion Criteria:

Subjects meeting all of the following criteria will be considered for enrollment in the study:

- 1. Male and female patients aged ≥ 18
- 2. Subjects with Compensated Chronic Liver Disease, defined as child 5-7.
- 3. Patients with mild disturbance of liver biochemical profile by one of the following criteria: (elevated Total Serum Bilirubin ≤ 3 mg/dl, or elevated Direct Serum Bilirubin ≤ 2 mg/dl, or elevated one or more of liver enzymes up to 3 times of the normal level).: (Alanine Transaminase (ALT), Aspartate Aminotransferase (AST), Alkaline Phosphatase (AIP) & Gamma Glutamyl Transpeptidase (GGT)).
- 4. Non-diabetic subjects and subjects with Controlled DM-type 1 and 2 patients, HbA1C up to 7.5%
- 5. Non-pregnant or lactating female patients

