6 ASSESSMENT SCHEDULE

Subjects will be enrolled for duration of 6 months including the screening visit

- Screening visit 1 (Treatment initiation)
- Visit 2: after 1st month, follow-up 1
- Visit 3: after 2nd month, follow-up 2
- Visit 4: after 3rd month, follow-up 3
- Visit 5: after 4th month, follow-up 4
- Visit 6: after 5th month, follow-up 5

7 Determination of Sample Size:

As the primary objective is to assess the efficacy of Ursoplus[®] capsules (UDCA 250mg & Silymarin 140mg) versus UDCA alone versus Placebo among Egyptian NASH Patients in reduction of total serum bilirubin, and based on the previous study of [the hepatoprotective effect of Silymarin and UDCA in CHC patients][i], which have been conducted on 40 patients; 10 patients received silymarin, 10 patients received UDCA, 10 patients received Silymarin + UDCA and 10 patients received Placebo.

And this study showed that:

The 12 weeks treatment period of Placebo did not show significant improvement regarding T Bilirubin levels $1.6 \pm 1.0 \text{ Vs.} 1.8 \pm 0.7$, p=0.166

A statistically significant improvement in mean \pm SD serum T bilirubin levels 1.3 \pm 0.5 vs. 1.2 \pm 0.5, p = 0.016 was obtained with 500mg/day UDCA therapy

In addition, the mean \pm SD; T. bilirubin levels for the combined therapy group (Silymarin + UDCA) decreased significantly 1.4 \pm 0.1 vs. 1.2 \pm 0.3, p= 0.022

Given that a researcher has the null hypothesis that $\mu=\mu 0$ and alternative hypothesis that $\mu=\mu 1\neq \mu 0$, and that the population variance is known as $\sigma 2$. Also, he knows that he wants to reject the null hypothesis at a significance level of α which gives a corresponding Z score, called it $Z\alpha/2$. Therefore, the power function will be

```
P\{Z > Z\alpha/2 \text{ or } Z < -Z\alpha/2|\mu 1\} = 1-\Phi[Z\alpha/2-(\mu 1-\mu 0)/(\sigma/n)]+\Phi[-Z\alpha/2-(\mu 1-\mu 0)/(\sigma/n)].
```

So, the following parameters are used to calculate the expected sample of the study:

Design: F tests - ANOVA: Fixed effects, omnibus, one-way, Analysis: A priori: Compute required sample size

• Input:

o Effect size f = 0.2124591 o α err prob = 0.05 o Power (1- β err prob) = 0.863 o Number of groups = 3

[figure not shown]
Output:

[figure not shown]
Non-centrality parameter λ = 12.1874947
 Critical F = 3.0295971
 Numerator df = 2
 Denominator df = 267

Denominator df
 Total sample size
 Actual power
 267
 270
 0.8697572

- Confidence level 95% (α error = 5%)
- Study Power = 87%

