- Sample Size = 270 Subjects (1:1:1)
- Drop out = 10% (27 subjects)
- Total number of patients: 297 subjects.
- Ursoplus Sample Size =99 subjects

- Placebo Sample Size = 99 subjects
- UDCA Sample Size = 99 subjects

8 Randomization:

Randomization is done using Stratified random sampling according to Vibration-controlled transient elastography in screening visit:

Group with non-cirrhosis (group1), F0, F1 and F2.

Group with advanced fibrosis and cirrhosis (group2), F3 and F4.

Subjects will be randomized into the 3 treatment groups with a balanced ratio of 1:1:1 by Data Management department (DM) of CRO (Nagy Research). The number of patients of the three treatment groups will be balanced (ratio 1:1:1). (99 Ursoplus[®]: 99 UDCA: 99 Placebo). Figure 1 shows Stratified Random Sample

[figure not shown]

Figure 1: Stratified Random Sampling

9 Blinding

NA, as study is open label.

10 Code-Breaking:

NA

11 Data Analysis:

11.1 Test for Normality, reliability and validity:

Normality, reliability and validity tests are to be done before the main data analysis, to choose the appropriate statistics and significant tests that will be used.

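### All efficacy results come only from completers without a protocol violation, so this open-label three-arm comparison can be biased in either direction and the plan has no analysis that would show it

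*SAP*

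**What the plan says.** SAP section 11.2 defines two populations. For efficacy: "Analysis of all efficacy variables will be performed only for patients who completed the study without protocol violation (as per protocol"). For safety: "Analysis of all safety variables will be performed for all patients (intent-to-treat population"), meaning everyone who took at least one dose. The only set called intent-to-treat is therefore a treated set, and it is not used for efficacy.

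SAP sections 11.3 and 11.4 and the efficacy table shells (Tables 3 to 11) add no all-randomised efficacy analysis, no sensitivity analysis and no method for missing values. Protocol violation is not defined in the available text.

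The design section opens: "This is a Prospective, Multi center, open-label, randomized, control, Interventional, phase IV Study". Section 9 (Blinding) reads: "NA, as study is open label". One of the three arms receives placebo.

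The Study Completion page of the case report form lists the reasons for leaving early. Besides adverse events and the participant's own decision, they include "Disease progression which requires discontinuation of the study medication" and "Significant non-compliance with treatment regimen or study requirements". SAP section 7 allows for losses with "Drop out = 10% (27 subjects").

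**The concern.** Randomisation makes the three arms comparable at entry. Restricting the analysis to patients who finish without a violation selects on events that mostly happen later. Progression, adverse events and poor compliance can be related to the liver tests being analysed, and they can differ by arm. Because the arm is known, that knowledge can influence who leaves and what is judged a violation. Laboratory endpoints do not prevent this: the problem is who is analysed, not how bilirubin is measured.

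The arm that loses more of its poor-outcome patients looks better than it is. The restriction governs all six primary laboratory variables and every secondary efficacy result.

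A secondary point: the 10% allowance covers drop-out, but the efficacy set also removes completers with violations, so the analysed number can fall below the one planned.

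**Working it through.** **Inputs from SAP section 7:** "Effect size f = 0.2124591", alpha 0.05, three groups, 270 evaluable, 297 randomised (99 per arm). The cited earlier study gives total bilirubin changes of +0.2 (placebo, 1.6 to 1.8), −0.1 (UDCA, 1.3 to 1.2) and −0.2 (combination, 1.4 to 1.2) mg/dl.

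**The plan's own figures.** λ = N·f² = 270 × 0.2124591² = 12.187 and critical F(2, 267) = 3.0296, both as printed. The noncentral F power is 88.5%, against the stated 87.0%. I use 88.5% for like-for-like comparisons.

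**Implied SD.** The three changes have mean −0.0333 and squared deviations summing to 0.08667, so their SD is √(0.08667/3) = 0.16997. Then 0.16997/0.2124591 = 0.800 mg/dl. The plan does not state this SD, but it returns f to the printed digits.

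**Bias.** Suppose excluded patients average D worse than retained ones, and a fraction p of the arm is excluded. The retained mean differs from the full-arm mean by p·D, so the bias between two arms is D × (difference in p). D and p are assumptions, not figures from the documents.

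| D (mg/dl) | Gap in p | Bias (mg/dl) | Share of Ursoplus–UDCA (0.1) | Share of UDCA–placebo (0.3) | Share of Ursoplus–placebo (0.4) |
|---|---|---|---|---|---|
| 0.4 | 0.05 | 0.02 | 20% | 7% | 5% |
| 0.4 | 0.10 | 0.04 | 40% | 13% | 10% |
| 0.8 | 0.10 | 0.08 | 80% | 27% | 20% |

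**False-positive rate with no true effect** (bias b in one arm, SD 0.80, noncentral F). With equal arms of n, λ = n·(2/3)·b²/0.64. For n = 90, λ is 0.0375, 0.15 and 0.60.

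| Bias (mg/dl) | Pooled ANOVA, 90 per arm | Pooled ANOVA, 79/89/89 | One pairwise z test, 90 per arm |
|---|---|---|---|
| 0.02 | 5.3% | 5.3% | 5.3% |
| 0.04 | 6.1% | 6.0% | 6.3% |
| 0.08 | 9.7% | 9.3% | 10.3% |

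**Simulation checks, no treatment effect:**
- Outcome-related exclusion of 20/10/10% (20,000 trials) gives bias 0.039 and 0.080 mg/dl, with ANOVA error 6.3% and 9.8%.
- Equal exclusion of 10% or 20% by the same process gives 4.7% to 5.1%.
- All randomised patients with complete data give 4.9% to 5.3%.
- Equal rates are not enough if the reasons differ. With 10% lost in every arm, related to outcome in one arm only (correlation 0.3 or 0.5; 8,000 trials), the error is 6.6% or 9.7%. With correlation zero it is about 5%.

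**Secondary point, power at the plan's f.** Losing 10% of 297 leaves 267 patients and 88.1% power; 20% leaves 237 and 83.7%; 30% leaves 207 and 78.1%. Against 88.5% at 270, losses of 20% to 30% cost about 5 to 10 points.

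**The case against.** The strongest objections concern size and remedy, because the wording of section 11.2 is explicit.

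- **The illustration is not the tabulated test.** It uses mg/dl change in one pooled ANOVA, whereas section 11.4.1 makes percent change primary and Tables 3 to 8 give p-values within each fibrosis group. This stands. With an assumed even split (45 per arm per group), biases of 0.04 and 0.08 give 5.6% and 7.3%.
- **The assumptions are strong.** A deficit of 0.4 to 0.8 mg/dl is 0.5 to 1.0 SD, and no document shows that exits differ by arm. This is also fair; the milder case in the tables gives only 5.3%.
- **Imputation repairs little by itself.** Liver tests are on the forms only at screening and week 24. If exit depends on outcome and the data are roughly normal, adjusting for baseline leaves about 1 − ρ² of the bias, where ρ is the baseline–outcome correlation: 91% at ρ = 0.3 and 75% at ρ = 0.5. This stands and shapes the fix.
- **The text may already allow more.** Section 11.4 mentions the overall sample, but in contrast to the two fibrosis groups, and that does not override the word "only" in 11.2. Section 11.3 announces a final SAP before database lock, but it starts from these specifications. The available protocol document consists of case report form pages, so the finding is limited to the plan as available.

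**Conclusion.** The concern holds and should be fixed before the data are analysed. The case rests on the design: a stated rule limits every efficacy result to a set chosen after randomisation in an open-label trial, and nothing in the plan would reveal whether the choice mattered.

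The numbers illustrate and do not predict. They rest on an SD of 0.80 mg/dl implied by the plan's f and on assumed exclusions. Over the range shown, the bias is 0.02 to 0.08 mg/dl and the pooled false-positive rate 5.3% to about 10%. The contrast most exposed is Ursoplus against UDCA, which isolates silymarin and has a planning difference of only 0.1 mg/dl. Neither the direction nor the actual size can be known from the documents, and if exclusion follows the same process at the same rate in every arm the error rate stays near 5%.

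**What to change.** In SAP section 11.2:

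1. Make all randomised patients, analysed in their assigned arm, the primary efficacy population.
2. Keep per-protocol as a sensitivity analysis, with violations listed and defined before the data are analysed.
3. Seek week-24 laboratory values from patients who stop study drug, where consent allows.
4. For values still missing, use multiple imputation by arm with baseline value and fibrosis stratum, adding collected data such as week-12 RAND-36 scores, adverse events and withdrawal reason where useful. Add a delta (tipping-point) analysis, because imputation alone cannot remove outcome-related loss.
5. Record the change in the final SAP that section 11.3 announces.

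**Cost.** Some extra analysis work and one change in conduct: the withdrawal page has no laboratory fields. Bringing back completers with violations needs no new data. The week-24 values are the urgent part, since they cannot be recovered later.

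The estimated effect may shrink. If drop-outs gain no treatment benefit, so that f is multiplied by (1 − drop-out), power with all 297 values observed is 84.4% at 10% drop-out, 74.5% at 20% and 62.1% at 30%. With 10% drop-out and only 267 values observed it is about 80%. Holding the plan's 86.3% target with every value observed would take 315 patients at 10% drop-out or 396 at 20%. Stating the lower power is an acceptable alternative to enrolling more.

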Spleen	Normal		Abnormal			
lf abnormal,						
findings:	Splenic Vein Diameter:mm					
Gall Bladder	Normal		Abnormal			
lf abnormal,						
findings:	Common B	ile Duct (CBD) Diame	ter:mm (Ν. ι	ıp to 6mm)		

Patient's		Patient's	Screening Visit
Nº:		Initials:	Initiation Visit

Vibration-controlled transient elastography with CAP (Fibroscan)

Date of Fibroscan: ___/ ___/ (DD / MMM / YYYY)

	Liver stiffness measurement	Fi	broscan score	
Liver		F0/F1	F2	
		F3	F4	
If abnormal, findings:				
Safety Laboratory Tests				

Date of Laboratory Tests: __/ __/ (DD / MMM / YYYY)

Laboratory Parameter	Value	Unit	If parameter indicated as out of normal range on report, please check if clinically significant:
ALT			🗌 No 🔄 Yes
AST			□ No □ Yes
Alkaline Phosphatase (ALP)			□ No □ Yes
Gamma-GT			□ No □ Yes
Total Bilirubin			□ No □ Yes
Direct bilirubin			□ No □ Yes
S Albumin			□ No □ Yes
РТ			□ No □ Yes
HbA1c for diabetic patients			□ No □ Yes
PCR/ Antibody for hepatitis C			□ No □ Yes
HBs Ag			□ No □ Yes
Serum β -HCG (for Females in child bearing period)			□ No □ Yes

Patient's		Patient's		Screening Visit
Nº:		Initials:		Initiation Visit

Assessment for quality of life (The RAND 36-Item Health Survey)

Completed

Not Completed

End of Screening Visit

End	of Screening Visit Checklist:	Yes	No
1.	Does the participant meet the inclusion and exclusion criteria to date?		
2.	Have all Screening Visit procedures been completed?		
3.	Have the Medical History and Concomitant Medication pages been completed?		

Participant's eligibility:
Is the participant eligible to take part in the Clinical Study?
☐ Yes
□ No, Please give reason for screen failure below
Reason(s) for screen failure:
1.
2.
Investigator Sign-Off
Investigator's Name:
Investigator's Signature: Date ://
(DD / MMM / YYYY)

Patient's Nº:		Patient's Initials:		Scre Initi	ening Visit ation Visit		
	Randomization						
Group A	A	Group B		Group C			
			·				
Drug Dispense							

Date of Drug Dispense: ___/ ___ (DD / MMM / YYYY)

Drugs are dispensed for the patient to be sufficient for 30 days of treatment The subject is asked to take the treatment daily and come next visit with the empty blisters after 30 days, with a window of 7 days.

Drug Dispense	Number of Capsules	Number of Blisters
Drug A, B, or C		

Investigator's Name:

Investigator's Signature: _____ Date: ___/ ___/

(DD / MMM / YYYY)

Visit 2 (Week 4) (may be done by phone call)

Date of Visit 2: ___/ ___ (DD / MMM / YYYY)

Vital Signs

Vital Signs & Weight:

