11.3 Statistical methods

This section provides specifications for preparation of final Statistical Analysis Plan (SAP), which will be issued prior to database lock. Any differences compared to this statistical section should be identified and documented in final SAP. Analysis will be done using SPSS version 21.

Categorical variables will be presented by number and percentage. Chi square test (or its subsidiaries) will be used to determine the p value. P -value <0.05 is considered significant.

Numerical Parametric variables will be presented by mean, SD and range. Paired ttest will be used to determine p-value between before and after treatment. Repeated measure ANOVA will be used to calculate significant effect for each group independently from baseline to end of treatment. One-way ANOVA test will be used to show and determine p-value and significance between 3 treatment groups at each point.

Numerical Non-Parametric variables will be presented by Median and interquartile range. Wilcoxon Sign Rank test will be used to determine p-value between before and after treatment. Friedman test will be used to calculate significant effect for each group independently from baseline to end of treatment. Kruskal-Wallis test will be used to show and determine p-value and significance between 3 treatment groups at each point.

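### Efficacy is analysed only in completers without protocol violation, so in this open-label trial the comparison of arms depends on who leaves after randomisation

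*SAP*

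**What the plan says.** SAP 11.2 gives one efficacy set: "Analysis of all efficacy variables will be performed only for patients who completed the study without protocol violation (as per protocol". The same section takes a broader view of safety: "Analysis of all safety variables will be performed for all patients (intent-to-treat population) who received even 1 dose of the treatment". The SAP contains no all-randomised, modified intent-to-treat or sensitivity analysis of efficacy. It does not define protocol violation and names no missing-data method.

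SAP 2 describes the trial: "This is a Prospective, Multi center, open-label, randomized, control, Interventional, phase IV Study". SAP 9 confirms that there is no blinding.

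The supplied protocol document is a case report form. Its Study Completion page first asks whether the participant completed the trial. Only a negative answer leads to the early-withdrawal reasons, which include "Disease progression which requires discontinuation of the study medication or results in inability to continue to comply with study procedures" and "Significant non-compliance with treatment regimen or study requirements". Adverse events, the investigator's decision and ineligibility arising during the study are also listed.

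The "Safety Laboratory Tests" section with the bilirubin and enzyme fields appears at screening and at the Week 24 visit only, as does FibroScan. RAND-36 is also completed at Week 12. The unscheduled-visit form has no laboratory section.

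SAP 11.3 presents the statistical section as the specification for a "final Statistical Analysis Plan (SAP), which will be issued prior to database lock".

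**The concern.** Randomisation makes the arms comparable on the day patients are assigned. A set defined by completion and compliance is formed afterwards, and the arms within it need not be comparable.

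Two distortions are possible. If one arm truly does worse, more of its worsening patients may leave. Those who remain look more like the other arms, and part of the effect is hidden. If the arms do not differ but staff act on worsening more readily in one of them, a false gap appears, in either direction. Judgements about non-compliance or violation made with the arm known can do the same.

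The data are also at risk. A patient who leaves before Week 24 has no post-baseline bilirubin or enzyme value on the form. A later change of analysis set cannot recover a value that was never collected.

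**Working it through.** **Inputs from SAP 7.** f = 0.2124591, alpha 0.05, three groups, 270 evaluable, 27 dropouts, 297 randomised (99 per arm).

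**Step 1: the plan's own figure.** The non-centrality is N·f² = 270 × 0.2124591² = 12.1875, and the critical F on 2 and 267 df is 3.0296. Both match the SAP. The omnibus power is then 0.885, against the SAP's 0.870.

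**Step 2: power does not require the restriction.** With f unchanged, power is 0.881 at 297 × 0.9 ≈ 267 completers and 0.914 at 297 randomised. f could be smaller once off-drug patients are included.

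**Step 3: selective exit when the arms differ.** The documents give no exit rates or correlations, so the following are assumptions.
- On-study status X is normal with arm mean μ and SD 1 (higher is worse). The Week 24 value has the same mean and SD and correlates ρ with X.
- A patient whose X exceeds a common cut c is removed with probability d, from 0.25 to 0.5.
- A quarter to a half of the 27 dropouts leave this way (6.75 to 13.5). The rest leave at random, and 270 are analysed.
- f fixes the outer gap at 3f/√2 = 0.451 SD if the active arms are equal, or 2f√1.5 = 0.520 SD if the arms are evenly spaced.

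With φ the normal density and Q the upper-tail probability, the mean of those kept is μ − ρ·d·φ(c−μ) / [1 − d·Q(c−μ)]. The cut solves 99·Σ d·Q(c−μ) = exits.

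Example: active arms equal, d = 0.5, ρ = 0.3, 13.5 exits.
- The cut is c = 1.516. Check: 99 × 0.5 × (0.0647 + 0.0647 + 0.1433) = 13.5.
- Active arms: 0 − 0.15 × 0.1264 / 0.9676 = −0.0196.
- Placebo: 0.4507 − 0.15 × 0.2261 / 0.9284 = 0.4142.
- The gap falls from 0.4507 to 0.4338, a shrinkage of 3.8%.

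| Assumed ρ | Shrinkage of gap | Power (0.885 without selective exit) |
|---|---|---|
| 0.2 to 0.3 | 1.1 to 3.8% | 0.857 to 0.878 |
| 0.2 to 0.8 | 1.1 to 10.0% | 0.831 to 0.878 |

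**Step 4: no true effect, unequal action.** All means are 0. The action rate is 0.25 in the active arms and 0.5 in placebo, or the reverse.

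Example: placebo at the higher rate, 13.5 exits, ρ = 0.8.
- Q = 13.5/99 = 0.1364, so c = 1.097 and φ = 0.2186.
- Active arms: −0.8 × 0.25 × 0.2186 / 0.9659 = −0.0453.
- Placebo: −0.8 × 0.5 × 0.2186 / 0.9318 = −0.0938.
- The false gap is 0.049 SD and the type I error is 0.061.

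This is the maximum over ρ from 0.2 to 0.8 with action rates of 25 to 50%. At ρ of 0.2 to 0.3 the type I error is 0.050 to 0.052.

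**Step 5: a different assumption.** A simulation under no effect (4,000 runs per scenario, Monte Carlo error about 0.7 points near 5%) removed the worst 5%, 10% and 15% of patients in the three arms, ranked on a score correlated r with outcome. Type I error was 5.6%, 7.8% and 12.6% at r = 0.3, 0.5 and 0.7. Equal 10% removal left the difference unbiased.

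The models in Steps 3 and 4 use a Week 24 level in one pooled test. The planned primary variable is percent change, and the table shells give p-values within each fibrosis group. The figures illustrate direction and rough scale only.

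**The case against.** The strongest reply concerns the mechanism. The Study Completion page codes why someone left; it does not make anyone leave. Nothing in the text bars a patient who has stopped drug from attending Week 24. Withdrawal rules may also exist in a protocol body that was not supplied. A reader might infer that the form itself turns a drug stop for progression into a trial exit. The documents do not support that.

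The outcome is also largely hidden from staff before Week 24. Bilirubin and enzymes are scheduled only at screening and Week 24, and four of the five visits between may be telephone calls. Staff would act mainly on symptoms or examination, so correlations of 0.6 to 0.8 are hard to justify. Entry is limited to Child 5-7 with enzymes at most 3 times normal, and treatment lasts 6 months, so progression may be uncommon.

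These points stand, and they limit the likely size. They do not touch the rule in SAP 11.2, which excludes every non-completer and every protocol violator whatever the reason.

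It can also be said that 270 evaluable patients suit a completer analysis and that a final SAP is still to come. The first settles the number analysed and does nothing about selection. The second means that the rule can still be changed, although nothing in the current text changes it.

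**Conclusion.** The concern holds as a defect of the stated analysis set. SAP 11.2 makes the only efficacy comparison depend on completion and compliance after randomisation, in a trial where staff know the arm, and the listed reasons for exit include outcome-related ones. The conclusion rests on that rule and does not need the modelled figures.

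The direction of bias is not fixed: greater removal of worsening patients on placebo works against Ursoplus, and greater removal on Ursoplus works in its favour. The size cannot be computed from the documents. The low-correlation shrinkage of about 1 to 4% and the type I ceiling of about 0.061 apply only under the assumptions shown.

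A reader might infer a large bias from the high-correlation row or from the simulation in Step 5. Those results need correlations that the laboratory schedule makes doubtful, or removal rates differing between arms by amounts that the documents do not give.

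**What to change.** 1. Amend SAP 11.2 so that the primary efficacy analysis includes every randomised patient in the assigned arm, regardless of drug discontinuation or protocol violation. Keep the per-protocol set as supportive.
2. Collect the planned Week 24 laboratory tests, FibroScan and RAND-36 from every patient who has not withdrawn consent, on or off drug.
3. Record the stop of study drug, with date and reason, separately from leaving the trial. The adverse-event log codes permanent withdrawal of drug but has no stop date; dated dispensing only brackets it. Keep an exit code for patients too ill to continue.
4. For patients still without a Week 24 value, impute using the reason for and timing of the exit as well as baseline value and fibrosis group. Baseline and fibrosis group alone carry no on-treatment information and would leave outcome-related exits uncorrected.
5. Add a sensitivity analysis that assigns worse values to patients who died or left for worsening.

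The cost is an SAP edit before the final version, one added form item and a short site instruction, with no visit or test beyond the planned Week 24 visit. Item 2 must take effect while patients are still on study. Safety decisions to stop drug are unchanged. The downside is that off-drug patients may dilute the on-drug effect.
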